8.4 Pharmacokinetics, [REDACTED] and Immunogenicity

The PK, ADA [REDACTED] samples will be collected as per the SoE ([Table 1](#) and [Table 2](#)). Additional biological samples may be collected by the Investigator when clinically indicated (e.g., at the time of significant AEs that are at least possibly related to the study drug) and may be used for PK [REDACTED] testing.

When multiple samples are required at the same time point, collection of safety samples should be first, followed by PK, then ADA [REDACTED]

In order to better understand the disease, metabolic disposition, and pharmacologic behavior of loncastuximab tesirine in humans, samples remaining after primary analyses may be utilized for further analysis.

Biological samples may be retained for up to 10 years to further address scientific questions as new information in regard to the disease or the study drug becomes available.

For detailed instructions related to central laboratory sample collection, labeling, processing, storage, or shipment refer to the appropriate laboratory manual(s).

8.4.1 Pharmacokinetics

The PK profile of loncastuximab tesirine (total antibody), PBD-conjugated antibody, and unconjugated warhead SG3199 will be assessed by a central laboratory designated by the Sponsor using validated bioanalytical methods.

Approximately 6 mL of whole blood will be collected as per [Table 1](#) and [Table 2](#) and [Table 11](#) and [Table 12](#).

Blood should be drawn from a vein away from the one used for study drug infusion.

PK samples must be stored at $\leq -70^{\circ}\text{C}$. Please refer to the laboratory manual for detailed instructions regarding specimen handling and shipment.

At time points coinciding with ECG collection, PK blood collection should occur immediately after the end of the ECG recording and, when applicable, after vital signs. If a patient experiences Torsade de Pointes, additional PK samples (e.g., unscheduled) should be collected.

Table 11 Sampling Schedule for PK and ADA: Phase 1

Cycle	Day	PK Time point (window)	ADA Time point (window)
C1	D1	Pre-dose (preferably within 2 h prior to start of infusion) EOI (-5 to +10 min) Post-dose* 4 h (\pm 10 min)	Pre-dose (preferably within 2 h prior to start of infusion)
	D8	Post-dose* 168 h (\pm 48 h)	-
	D15	Post-dose* 336 h (\pm 48 h)	Post-dose* 336 h (\pm 48 h)
C2	D1	Pre-dose (within 2 h prior to start of infusion) EOI (-5 to +10 min) Post-dose* 4 h (\pm 10 min)	Pre-dose (within 2 h prior to start of infusion)
	D8	Post-dose* 168 h (\pm 48 h)	-
	D15	Post-dose* 336 h (\pm 48 h)	-
C3	D1	Pre-dose (prior to ibrutinib dosing)	Pre-dose (prior to ibrutinib dosing)
C5 and C6 (only for patients receiving loncastuximab tesirine in C5 and C6)	D1	Pre-dose (preferably within 2 h prior to start of infusion)	Pre-dose (preferably within 2 h prior to start of infusion)
C7 (patients receiving loncastuximab tesirine for C5 and C6)	D1	Pre-dose (prior to ibrutinib dosing)	Pre-dose (prior to ibrutinib dosing)
EOT		At any time during visit day	At any time during visit day
Unscheduled		Any time	Any time (if applicable, close to PK sample)

Abbreviations: ADA, anti-drug antibody; EOI, end of infusion; EOT, end of treatment; PK, pharmacokinetics.

*Post-dose time point is counted from start of infusion.

Table 12 Sampling Schedule for PK and ADA: Phase 2

Cycle	Day	PK Time point (window)	ADA Time point (window)
C1	D1	Pre-dose (preferably within 2 h prior to start of infusion) EOI (-5 to +10 min) Post-dose* 4 h (\pm 10 min)	Pre-dose (preferably within 2 h prior to start of infusion)
	D8	Post-dose* 168 h (\pm 48 h)	-
	D15	Post-dose* 336 h (\pm 48 h)	Post-dose* 336 h (\pm 48 h)
C2	D1	Pre-dose (within 2 h prior to start of infusion) EOI (-5 to +10 min) Post-dose* 4 h (\pm 10 min)	Pre-dose (within 2 h prior to start of infusion)
	D8	Post-dose* 168 h (\pm 48 h)	-
	D15	Post-dose* 336 h (\pm 48 h)	-
C3	D1	Pre-dose if loncastuximab tesirine is dosed (preferably within 2 h prior to start of infusion)	Pre-dose if loncastuximab tesirine is dosed (preferably within 2 h prior to start of infusion)
C5 and C6	D1	Pre-dose (preferably within 2 h prior to start of infusion)	Pre-dose (preferably within 2 h prior to start of infusion) C5 only**
C7	D1	Pre-dose if loncastuximab tesirine is dosed (preferably within 2 h prior to start of infusion)	Pre-dose if loncastuximab tesirine is dosed (preferably within 2 h prior to start of infusion)
C9 and C10	D1	Pre-dose (preferably within 2 h prior to start of infusion)	Pre-dose (preferably within 2 h prior to start of infusion) C9 only**
C11	D1	Pre-dose if loncastuximab tesirine is dosed (preferably within 2 h prior to start of infusion)	Pre-dose if loncastuximab tesirine is dosed (preferably within 2 h prior to start of infusion)
C13	D1	-	Pre-dose (preferably within 2 h prior to start of infusion) for loncastuximab tesirine given at every cycle in combination with ibrutinib only
EOT		At any time during the visit day	At any time during the visit day
Unscheduled		Any time	Any time (if applicable, close to PK sample)

Abbreviations: ADA, anti-drug antibody; EOI, end of infusion; EOT, end of treatment; PK, pharmacokinetics.

*Post-dose time point is counted from start of infusion.

**Applicable to protocol amendment version 5 and beyond.

To understand the metabolic disposition of loncastuximab tesirine in humans, samples remaining after PK analysis is complete may be pooled among patients for potential metabolite identification.

8.4.2 Immunogenicity

Detection of ADAs will be performed by using a screening assay for identification of antibody positive samples/patients, a confirmation assay, and titer assessment, and will be performed using the Meso-Scale Discovery Electrochemiluminescence platform (MSD-ECL). If an ADA is confirmed, a functional assay for the assessment of the neutralizing capacity of the ADA will be performed.

Approximately 6 mL of whole blood will be collected as per [Table 1](#) and [Table 2](#) and [Table 11](#) and [Table 12](#). Blood should be drawn from a vein away from the one used for study drug infusion.

For patients who test positive for ADAs, an additional ADA sample will be requested for testing every 12 weeks following the EOT visit until the ADA titer falls to a background level.

ADA samples must be stored at $\leq -70^{\circ}\text{C}$. Please refer to the laboratory manual for detailed instructions regarding specimen handling and shipment.

8.5 Patient-Reported Outcomes Questionnaires

The impact of study treatment on disease- and treatment-related symptoms, as well as various aspects of patient's health-related quality of life (HRQoL), will be assessed by three questionnaires:

- European Organization for Research and Treatment of Cancer (EORTC) Quality of Life Questionnaire (QLQ)-Core 30 (C30), [Section 13.4 \(Appendix 4\)](#).
- Lymphoma subscale (LymS) of Functional Assessment of Cancer Therapy – Lymphoma (FACT-Lym), [Section 13.5 \(Appendix 5\)](#).
- EuroQoL-5 Dimensions-5 Levels (EQ-5D-5L), [Section 13.6 \(Appendix 6\)](#).

Questionnaires will be completed in the respondent's native language, at the scheduled time points prior to the patient's clinical assessment and treatment. Patients will provide responses at the study site or by phone (i.e., the collection of EQ-5D-5L post disease progression). The patient should be given instructions, space, time, and privacy to complete the questionnaires by themselves and without any assistance from anyone else. The study coordinator should encourage the patient to complete the questionnaires without any missing responses.

8.5.1 European Organization for Research and Treatment of Cancer Quality of Life Questionnaire – EORTC QLQ-C30

The European Organization for Research and Treatment of Cancer (EORTC) quality of life questionnaire (QLQ)-C30 is a validated and widely used questionnaire to assess quality of life of cancer patients. It is composed of 30 items assessing 15 domains, including five functional scales (physical, role, emotional, cognitive, and social), three multi-item symptoms (fatigue, nausea/vomiting, and pain), six single-item symptoms (dyspnea, insomnia, appetite loss, constipation, diarrhea, and financial difficulties), and one global health status/ quality of life (QoL) scale. All scales range from 0 to 100 after applying a linear transformation to raw scores. Higher scores in functional scales and global health status/ QoL scales indicate a better HRQoL whereas higher scores in symptom scales indicate more severe symptoms ([Aaronson NK et al, 1993](#)). Patients will complete this questionnaire as per the SoE ([Table 2](#)).

8.5.2 Lymphoma Subscale (LymS) of FACT-Lym

FACT-Lym is a HRQoL questionnaire validated in patients with NHL. It consists of a general HRQoL assessment (FACT-G) and a disease-specific subscale (LymS). FACT-G (27 items) measures physical well-being, social/family well-being, emotional well-being, and functional well-being. The LymS (15 items) addresses symptoms and functional limitations that are important to patients with NHL, such as lumps and swelling in certain parts of the body, fever, night sweats, itching, and weight loss. Patients are asked to respond to each item with a score of 0–4, where 0 = not at all, 1 = a little bit, 2 = somewhat, 3 = quite a bit, and 4 = very much. To ease burden on patients, only LymS will be collected and consequently LymS summary score be reported in this trial. The LymS summary score ranges from 0 to 60, with higher scores indicating better HRQoL. ([Hlubocky et al, 2013](#)). Patients will complete this questionnaire as per the SoE ([Table 2](#)).

8.5.3 EuroQol-5 Dimensions-5 Levels (EQ-5D-5L)

EQ-5D-5L is designed as an international, standardized, generic instrument for describing and evaluating HRQoL ([Herdman et al., 2011](#)). The EQ-5D-5L consists of 2 parts:

- a. The descriptive system comprises five dimensions with 1 question for each dimension: mobility, self-care, usual activities, pain/discomfort, and anxiety/depression. Each dimension has five levels of perceived problems: no problems, slight problems, moderate problems, severe problems, unable to/extreme problems. The descriptive system can be converted into a health utility index for economic evaluation.
- b. The visual analog scale (VAS): patients rate their current general health state on a scale ranging from 0 (worst health that can be imagined) to 100 (best health that can be imagined).

Patients will complete this questionnaire as per the SoE ([Table 2](#)).

9 STATISTICAL CONSIDERATIONS

Full details of the analysis plan, including a more technical and detailed elaboration of the statistical analyses, will be provided in the statistical analysis plan (SAP). [REDACTED]

9.1 Sample Size

The study will enroll approximately 243 patients. Phase 1 will enroll up to 55 patients and Phase 2 will enroll approximately 188 patients.

9.1.1 Phase 2 Sample Size Calculation for non-GCB DLBCL Cohort Where Loncastuximab Tesirine is Given Intermittently in Combination with Ibrutinib

The primary hypothesis is that the CRR based on central review for patients treated with loncastuximab tesirine and ibrutinib is significantly greater than 20% (i.e., $H_0: p \leq 0.2$ vs. $H_a: p > 0.2$). This hypothesis will be tested at type I error of 0.05 (two sided).

Simon's 2-stage design ([Simon, 1989](#)) will be used. The null hypothesis that the true CRR is 0.2 will be tested against a one-sided alternative. In the first stage, 22 patients will be accrued. If there are 5 or fewer CRs in these 22 patients, this cohort will be stopped. Otherwise, 44 additional patients will be accrued for a total of 66. The null hypothesis will be rejected if 20 or more CRs are observed in 66 patients. This design yields a type I error rate of 0.05 and power of 90% when the true CRR is 0.4.

9.1.2 Phase 2 Sample Size Calculation for the Cohort Where Loncastuximab Tesirine is Given at Every Cycle in Combination with Ibrutinib

The primary hypothesis is that the CRR is based on central review for patients treated with the re-determined RP2D of loncastuximab tesirine and ibrutinib combination is significantly greater than 30% (i.e., $H_0: p \leq 0.3$ vs. $H_a: p > 0.3$). This hypothesis will be tested at type I error of 0.05 (two sided).

A Two-stage design with futility monitoring ([Zeng et al., 2015](#)) will be used. The null hypothesis that the true CRR is 0.3 will be tested against a one-sided alternative. In the first stage, 60 patients will be accrued. If there are 20 or fewer CRs in these 60 patients, this cohort will be stopped. Otherwise, 40 additional patients will be accrued for a total of 100. The null hypothesis will be rejected if 40 or more CRs are observed in 100 patients. This design yields a type I error rate of 0.05 and power of 85% when the true CRR is 0.45. Enrollment will continue during the interim analysis.

9.2 Analysis Populations

- The Safety population will consist of all patients who receive study drug.
- The DLT-evaluable population will consist of all patients in Phase 1 dose escalation, who receive study drugs, and will exclude patients who discontinue from the study during the DLT Period without experiencing a DLT.
- The Efficacy population will consist of all patients who receive at least 1 dose of study drug, who have valid baseline disease assessment(s), and who have at least one valid post-baseline disease assessment. Patients who do not have a post-baseline assessment due to early clinical progression or death (after receiving study drug) will also be included.
- The PK population will consist of all patients who have at least 1 pre-(C1D1) and 1 post-dose valid PK assessment.
- [REDACTED]
- Per Protocol population: All patients in the Safety population without major protocol deviations, which will be further described in detail in the SAP.

9.3 Phase 2 Interim Analysis for Futility

9.3.1 Non-GCB Cohort Where Loncastuximab Tesirine is Given Intermittently in Combination with Ibrutinib

A single interim analysis is planned using Simon's 2 stage procedure (Simon, 1989) in the non-GCB DLBCL cohort where loncastuximab tesirine is given intermittently in combination with ibrutinib. The purpose of this interim analysis is solely to determine if there is a sufficient CRR observed early in the study to warrant continuing study enrollment to completion. The interim analysis constitutes a futility analysis; it will not be used to stop the trial early for positive efficacy. In the first stage of the study, an interim analysis will be performed at the time when the 22nd patient has two tumor assessments. Enrollment will continue during the interim analysis. If ≥ 6 patients achieve CR, the study will proceed to the second stage. If < 6 patients achieve CR, enrollment in this cohort will be halted.

9.3.2 Cohort Where Loncastuximab Tesirine is Given at Every Cycle in Combination with Ibrutinib

A two-stage design with futility monitoring (Zeng et al., 2015) is planned in the cohort given loncastuximab tesirine at every cycle in combination with ibrutinib for all DLBCL. The purpose of futility monitoring is solely to determine if there is a sufficient CRR observed early in the study to warrant continuing study enrollment to completion. Futility monitoring will not be used to stop the trial early for positive efficacy. In the first stage of the study, an interim analysis will be performed at the time when the 60th patient has two tumor assessments. Enrollment will continue during the interim analysis. If ≥ 21 patients achieve CR, the study will proceed to the second stage. If < 21 patients achieve CR, enrollment in this cohort will be halted.

9.4 Final Analysis

For primary and key secondary endpoints analyses, a database snapshot may be taken when all patients have a minimum of 6 months follow up after initial documented response. All efficacy, and safety endpoints will be analyzed and reported in the clinical study report (CSR). Results of the PK analysis will be reported separately in a PK report.

Follow-up analyses may be performed when all the patients complete the study per protocol.

9.5 Demographics and Baseline Characteristics

Demographics and baseline characteristics, such as medical/medications history and cancer history, will be summarized for the Safety population.

9.6 Exposure to Treatments

Exposure to study drug and prior and concomitant medications will be summarized for the Safety population. Dose interruptions, reductions, and relative dose intensity will also be summarized.

9.7 Efficacy Analyses

In the non-GCB DLBCL cohort, the primary efficacy analyses will be based on response as determined by the IRC.

Responses reported by investigators will be used for sensitivity analyses. Similarly, in other cohorts, responses by the IRC (if available) and by investigators will be summarized separately.

Efficacy analysis will be summarized in the non-GCB DLBCL, GCB DLBCL, and MCL cohort and in the combined DLBCL group (non-GCB plus GCB).

9.7.1 Complete Response Rate

CRR will be defined as the proportion of patients with a best overall response (BOR) of CR, according to the 2014 Lugano classification ([Cheson et al., 2014](#)). The BOR will be derived based on response assessment performed on or before the start of subsequent anti-cancer therapy.

The percentage of CRR with its 95% confidence interval (CI) will be presented.

9.7.2 Overall Response Rate

The ORR will be defined as the proportion of patients with a BOR of CR or PR, according to the 2014 Lugano classification. The overall response category will be derived based on response assessment performed on or before the start of subsequent anti-cancer therapy.

The percentage of ORR with its 95% CI will be presented. In contrast to CR, PR, or PD, a BOR of SD can only be made after the patient is on-study for a minimum of 35 days after the first dose of study drug. Any tumor assessment indicating SD before this time period will be considered as a non-evaluable for BOR if no assessment after this time period is available.

9.7.3 Duration of Response

DOR will be defined among responders (CR or PR) as the time from the earliest date of first response until the first date of either disease progression or death due to any cause. For patients who have not progressed or died at the time of the analysis, censoring will be performed using the date of the last valid disease assessment. The data will be analyzed by the Kaplan-Meier method. The median DOR and 95% CI will be presented. Further details will be outlined in the SAP.

9.7.4 Relapse-free Survival

Relapse-free survival (RFS) will be defined among CR patients as the time from the earliest date of first CR until the first date of either disease progression or death due to any cause. For patients who have not progressed or died at the time of the analysis, censoring will be performed using the date of the last valid disease assessment. The data will be analyzed by the Kaplan-Meier method. The median RFS and 95% CI will be presented. Further details will be outlined in the SAP.

9.7.5 Progression-free Survival

PFS will be defined as the time from first dose of study drug until the first date of either disease progression or death due to any cause. For patients whose disease has not progressed at the time of the analysis, censoring will be performed using the date of the last valid disease assessment. The data will be analyzed by the Kaplan-Meier method. The median PFS time and 95% CI will be presented. Further details will be outlined in the SAP.

9.7.6 Overall Survival

OS will be defined as the time from first dose of study drug until death due to any cause. For patients who have not died at the time of the analysis, censoring will be performed using the date the patient was last known to be alive. The data will be analyzed by the Kaplan-Meier method. The median OS and 95% CI will be presented. Further details will be outlined in the SAP.

9.8 Safety and Subgroup Analyses

Safety analyses will be presented descriptively

Subgroup analyses may be performed for CRR, ORR, DOR, RFS, PFS, and OS using the following variables if appropriate:

- Demographic variables: age group, gender, race, and country
- Baseline disease characteristics: tumor staging, and subtype
- Number of prior systemic therapies and response to prior systemic therapies

Other subgroup analysis factors may be evaluated as appropriate and the details will be provided in the SAP.

9.8.1 Adverse Events

The focus of AE summarization will be on TEAEs. A TEAE is defined as an AE that occurs or worsens in the period extending from the first dose of study drug to 30 days after the last dose of study drug or initiation of new anti-cancer therapy (whichever occurs first).

The TEAEs will be summarized. Summary tables will be presented to show the number of patients reporting TEAEs by severity grade and corresponding percentages. A patient who reports multiple TEAEs within the same Preferred Term (or System Organ Class) is counted only once for that Preferred Term (or System Organ Class) using the worst severity grade.

Separate summaries will be prepared for TEAEs classified as severe or life-threatening (Grade 3 or higher); study drug-related AEs; AEs leading to treatment interruption, modification, or discontinuation; SAEs; AESIs; and death.

9.8.2 Clinical Laboratory Results

Clinical hematology, coagulation panel, biochemistry, and urinalysis data will be summarized at each scheduled assessment. Shifts for clinical laboratory results that can be graded according to CTCAE v4.0 (or more recent) will be summarized by CTCAE grade. Shifts for other numeric laboratory results will be by high/normal/low flag. Shifts for all other laboratory results will be by normal/abnormal flag.

Summaries by visit will include data from scheduled assessments, and all data will be reported according to the nominal visit date for which it was recorded. Unscheduled data will be included in “worst case post-Baseline” summaries, which will capture a worst case across all scheduled and unscheduled visits after the first dose of study drug. Further details will be provided in the SAP.

9.8.3 Additional Safety Assessments

The results of scheduled assessments of vital signs, physical examinations, ECOG performance status, and 12-lead ECGs will be summarized. All data will be reported according to the nominal visit date for which it was recorded (i.e., no visit windows will be applied). Unscheduled data will be included in “worst case” summaries, which will capture a worst case across all scheduled and

unscheduled visits after the first dose of study drug. All data will be listed. Further details will be provided in the SAP.

9.9 Pharmacokinetic Analyses

The PK profile will include determination of: maximum concentration (C_{max}), time to C_{max} (T_{max}), area under the concentration-time curve from time zero to the last quantifiable concentration (AUC_{last}), area under the concentration-time curve from time zero to the end of the dosing interval (AUC_{tau}), area under the concentration-time curve from time zero to infinity (AUC_{inf}), apparent systemic clearance (CL), apparent volume of distribution (V_{ss}), apparent terminal half-life (T_{half}), and accumulation index (AI).

[figure not shown]
PK parameters will be determined for all PK-evaluable patients using a non-compartmental method with Phoenix WinNonlin (Certara USA, Inc., Princeton, NJ, US) or other appropriate software. Results of the PK analysis may be reported separately.

9.10 Immunogenicity Analyses

A tiered immunogenicity strategy (Figure 2) will be undertaken to evaluate ADAs by screening and confirmatory assays with titer evaluation, followed by characterization and evaluation of neutralizing capacity as needed. ADA sample collection, banking, and testing in validated and to be validated assays will be according to the [FDA Immunogenicity Testing of Therapeutic Protein Products —Developing and Validating Assays for Anti-Drug Antibody Detection Guidance for Industry \(Jan 2019\)](#).

Figure 2 Anti-drug Antibody Tiered Immunogenicity Testing Strategy

Abbreviations: ADA, anti-drug antibody; ADC, antibody drug conjugate; BSA, bovine serum albumin; mAb, monoclonal antibody; PK, pharmacokinetics.

Results from ADA testing will include tabular summarization for number/proportion of patients with positive pre-dose ADA response, number of patients with post-dose ADA response only, and number of patients with positive ADA response at any time. The denominator will be the total number of patients tested for ADAs in the study.

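### The post-dose-only ADA proportion is divided by all patients tested, including any who cannot be counted as post-dose only, so it is diluted by their share

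*Protocol*

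**What the plan says.** Protocol section 9.10 tabulates patients who are ADA-positive pre-dose, and then the "number of patients with post-dose ADA response only, and number of patients with positive ADA response at any time". The next sentence sets the base: "The denominator will be the total number of patients tested for ADAs in the study". It comes after all three rows and is not limited to any of them.

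The sampling times are in Protocol section 8.4.1, Table 11 (Phase 1) and Table 12 (Phase 2). The first ADA sample is taken before the first infusion on Cycle 1 Day 1. The first scheduled post-dose sample is on Cycle 1 Day 15, "Post-dose* 336 h". Later samples follow before dosing in certain cycles, with one at the end-of-treatment visit: "At any time during the visit day" in Table 12, with near-identical wording in Table 11.

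For pharmacokinetics, Protocol section 9.2 does set a condition on samples: "The PK population will consist of all patients who have at least 1 pre-(C1D1) and 1 post-dose valid PK assessment". No visible text sets a similar condition for ADA. The SAP lists ADA titers among the secondary endpoints for both phases (section 3), but shows no ADA analysis section. Its section 4.3 records no modification of the protocol's statistical section. One analysis set in SAP section 5.1 is blacked out; it cannot be checked and is not held against the plan.

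**The concern.** The post-dose-only row is the one a reader will take as the rate of ADA arising on treatment. Only a patient with a negative pre-dose result and at least one later result can be shown to belong there. The stated base is wider in two ways.

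- A patient whose only sample is the Cycle 1 Day 1 pre-dose one has been tested, and is in effect counted as negative for post-dose response.
- A patient who is already positive pre-dose cannot be post-dose *only*, but stays in the base.

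Both can occur under this protocol. Section 9.2 foresees treated patients who leave very early: "Patients who do not have a post-baseline assessment due to early clinical progression or death (after receiving study drug) will also be included". Exclusion criterion 1 removes only patients with a *known* positive ADA to a CD19 antibody, and section 9.10 itself provides a row for pre-dose positives.

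What is at stake is the accuracy of one descriptive proportion. The related secondary endpoint is ADA titers and, if applicable, neutralizing activity. No hypothesis, threshold or decision depends on the row.

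**Working it through.** The plan states no ADA rate or number tested, so there is no figure of its own to reproduce. The check is how the stated base relates to the at-risk base.

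**Inputs**

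- N, patients tested: not given. The SAP totals (section 4.1) stand in as upper values: 136 for the study and 89 for Phase 2.
- m, tested patients with no post-dose result or a positive pre-dose result, each counted once: not given. Assumed at 5, 10, 15 and 20% of N, rounded to whole patients.
- x, post-dose-only positives: not given. Assumed 5, with 14 as a higher case and 0 as a limit.
- Intervals: two-sided 95% Clopper-Pearson, the SAP's exact method (section 5).

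**Formulas**

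- Planned proportion = x / N
- At-risk proportion = x / (N − m)
- Planned / at-risk = (N − m) / N = 1 − f, where f = m / N

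So the planned figure is lower whenever m > 0 and x > 0, and the two agree if m = 0 or x = 0. This assumes that every one of the x positives has a negative pre-dose result.

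**Results for N = 136**

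| m (share) | N − m | Planned / at-risk | x = 5 | x = 14 |
|---|---|---|---|---|
| 0 (planned rule) | 136 | 1.000 | 3.7% (1.2–8.4) | 10.3% (5.7–16.7) |
| 7 (5%) | 129 | 0.949 | 3.9% (1.3–8.8) | 10.9% (6.1–17.5) |
| 14 (10%) | 122 | 0.897 | 4.1% (1.3–9.3) | 11.5% (6.4–18.5) |
| 20 (15%) | 116 | 0.853 | 4.3% (1.4–9.8) | 12.1% (6.8–19.4) |
| 27 (20%) | 109 | 0.801 | 4.6% (1.5–10.4) | 12.8% (7.2–20.6) |

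With x = 0 both proportions are 0%. The upper limit moves from 2.7% (N = 136) to 3.3% (109 at risk).

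**Results for N = 89, x = 5**

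- Planned: 5/89 = 5.6%
- m = 4 (5%): 5/85 = 5.9%
- m = 9 (10%): 5/80 = 6.25%
- m = 13 (15%): 5/76 = 6.6%

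**A case in the other direction.** Section 9.10 does not say that post-dose only requires a negative pre-dose *result*. A patient with no baseline sample and a positive later sample could be placed in that row. Suppose one of the 5 positives is such a patient and 14 others are not at risk. The at-risk figure is then 4 / (136 − 14 − 1) = 4/121 = 3.3%, and the planned 3.7% is too high.

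**The case against.** The strongest reply is that m may be close to zero. A patient who stops treatment before Day 15 is still asked to attend the end-of-treatment visit (Protocol section 7.1), where an ADA sample is scheduled. The gap is then limited to patients who die, withdraw or miss that visit before giving any later sample, plus pre-dose positives. The documents give no count, and the 5 to 20% shares are assumptions. This stands, and it is why the effect is probably small.

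Second, section 9.10 mentions a proportion only beside the pre-dose row, and a number for the other two. That is a fair reading of those words, but the denominator sentence follows all three rows and would have little purpose if only one were a percentage. The pre-dose-positive count is also tabulated, so a reader could subtract those patients. A reader could not do the same for patients without a post-dose result, because no row shows them.

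Third, the shift is small against sampling error: at most 0.9 points for 5 positives among 136 (3.7% to 4.6%), against an interval of 1.2 to 8.4%. This also stands.

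Three stronger readings are tempting, and the documents do not support them:

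- That immunogenicity *is* understated. This needs at least one patient not at risk and at least one post-dose-only positive, and neither is established.
- That the error is always downward. The missing-baseline case above goes the other way.
- That the any-time row should also require a post-dose result. A patient who is positive pre-dose and has no later sample is positive at some time and would be wrongly dropped. All tested patients is a suitable base there.

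**Conclusion.** The point holds for the post-dose-only row. The stated rule puts patients in the denominator who cannot reach the numerator, and no visible text in either document corrects it. The dilution factor is exactly 1 − f when every counted positive has a negative pre-dose result. With N = 136, 5 positives and an assumed 5 to 15% not at risk, 3.7% becomes 3.9 to 4.3%. With 14 positives, 10.3% becomes 10.9 to 12.1%. The number tested, the number of positives and the share not at risk are all assumptions, and the first is set at its largest possible value. If the share is zero, or there are no positives, the proportion does not change.

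This is a minor reporting point. It affects no primary inference, and the end-of-treatment sample probably keeps it small.

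**What to change.** State a base for each row in Protocol section 9.10, or in an ADA paragraph in the SAP:

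- **Pre-dose positive:** patients with a pre-dose ADA result.
- **Post-dose only:** patients with a negative pre-dose result and at least one post-dose result. This also stops a patient with no baseline sample from being counted here.
- **Positive at any time:** all patients tested, as now.

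Print each denominator in the table. If the sponsor wants continuity with the current rule, the all-tested base can be kept for the post-dose-only row as a supplementary figure.

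The cost is one sentence and a table footnote, with no new data. The downside is one extra denominator to explain and, in the usual case, a slightly less favourable figure.
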